1 SYNOPSIS

Not applicable.

2 SCHEDULE OF ACTIVITIES

Study assessments and procedures are presented in Table 2-1 and [Table 2-2](#).

Table 2-1: Screening Procedural Outline (IM101682)

Procedure	Screening Visit	Day -1 Visit	Notes
Eligibility Assessments			
Informed Consent	X		A participant is considered enrolled only when a protocol specific informed consent is signed.
Inclusion/Exclusion Criteria	X	X	
Medical History	X		Include any toxicities or allergy related to previous treatments.
Admission to the Clinical Facility		X	
Safety Assessments			
Physical Examination (PE)	X	X	If the screening PE is performed within 24 hours prior to dosing on Day 1 then a single exam may count as both the screening and predose evaluation. In addition to the PE, a skin exam will be conducted on Day -1. See Section 9.4.1.1 .
Physical Measurements	X	X	Includes height, weight, and BMI. Body weight only on Day -1.
Vital Signs	X	X	Includes body temperature, respiratory rate, and seated blood pressure and heart rate. Blood pressure and heart rate should be measured after the participant has been resting quietly in the seated position for at least 5 minutes.
Concomitant Medication Use	X	X	
12-Lead Electrocardiogram (ECGs)	X	X	ECGs should be recorded after the participant has been supine for at least 5 minutes.
Laboratory Tests			
Serology	X		Includes hepatitis C antibody, hepatitis B surface antigen (HBsAg), hepatitis B core antigen antibody (anti-HBc), and HIV-1 and -2 antibodies. Results must be available and reviewed prior to admission on Day -1.

Table 2-1: Screening Procedural Outline (IM101682)

Procedure	Screening Visit	Day -1 Visit	Notes
Urine Drug Test (Including Cotinine)	X	X	Screening results must be available and reviewed prior to admission on Day -1. Day -1 results must be available and reviewed prior to dosing on Day 1.
Alcohol Urine or Breath Test	X	X	Screening results must be available and reviewed prior to admission on Day -1. Day -1 results must be available and reviewed prior to dosing on Day 1.
Pregnancy Test (quantitative results)	X	X	For WOCBP only. Serum only. Screening results must be available and reviewed prior to admission on Day -1. Day -1 results must be available and reviewed prior to dosing on Day 1.
Follicle Stimulating Hormone (FSH)	X		Women only. Refer to Appendix 4 . Results must be available and reviewed prior to admission on Day -1.
Tuberculosis (TB) Screening	X		QuantiFERON [®] TB Gold test. A QuantiFERON-TB Gold test performed within 4 weeks of dosing on Day 1 is acceptable as long as there is documentation of a negative result.
Hematology and Serum Chemistry	X	X	Screening results must be available and reviewed prior to admission on Day -1. Day -1 results must be available and reviewed prior to dosing on Day 1. See Section 9.4.4 .
Thyroid Function Test	X		Thyroid-stimulating hormone (TSH) with reflex to free thyroxine (free T4), free triiodothyronine (free T3). Results must be available and reviewed prior to admission on Day -1.
Urinalysis	X	X	Screening results must be available and reviewed prior to admission on Day -1. Day -1 results must be available and reviewed prior to dosing on Day 1. See Section 9.4.4
Chest X-ray	X		A posterior-anterior and lateral chest x-ray will be performed. Results must be available and reviewed prior to admission on Day -1. See Section 9.4.7
Adverse Event Reporting			
Monitor for Serious Adverse Events	X	X	All SAEs must be collected from the date of participant’s written consent until 101 days post dose. If a participant prematurely discontinues, all SAEs must be collected 30 days post last visit.

Table 2-2: On Treatment Procedural Outline(IM101682)

Procedure	Day 1	Day 2	Day 4	Day 8	Day 15	Day 22	Day 29 ± 2 Days	Day 43 ± 2 Days	Day 57 ± 2 Days	Day 71 ± 2 Days Study Discharge ^a	Notes
Safety Assessments											
Physical Examination (PE)		X					X			X	
Targeted PE	X										Day 1 predose. Targeted examination of skin. Photographs may be taken of any areas affected by rash that develop after the start of the infusion (including evolving changes). See Section 9.4.1.1 . Continued monitoring of rashes will occur as needed. Targeted examination of other systems based on clinical symptoms.
Inspection of IV injection site	X										Predose and 1 hour post end of the infusion. Additional inspections (including photography of any changes) may be conducted as warranted. See Section 9.4.1.1.
Physical Measurements										X	Weight only.
Vital Signs	X ^b	X	X	X	X	X	X	X	X	X	See note in screening procedures.
Electrocardiogram (ECGs)	X ^c									X	See note in screening procedures.
	■	■	■	■	■	■	■	■	■	■	

Table 2-2: On Treatment Procedural Outline(IM101682)

Procedure	Day 1	Day 2	Day 4	Day 8	Day 15	Day 22	Day 29 ± 2 Days	Day 43 ± 2 Days	Day 57 ± 2 Days	Day 71 ± 2 Days Study Discharge ^a	Notes
Laboratory Tests											
Hematology and Serum Chemistry		X			X		X		X	X	See note in screening procedures and Section 9.4.4 .
Pregnancy Test					X		X		X	X	Serum quantitative results.
Adverse Event Reporting											
Monitor for Nonserious Adverse Events	X	X	X	X	X	X	X	X	X	X	All nonserious AEs must be collected at the start of study treatment on Day 1 through Day 71.
Monitor for Serious Adverse Events	X	X	X	X	X	X	X	X	X	X	See note in screening procedures.
Pharmacokinetic (PK) Assessments											
Blood PK Sampling	X	X	X	X	X	X	X	X	X	X	On Day 1, the blood sample should be drawn at predose. See Section 9.5.1 .

Table 2-2: On Treatment Procedural Outline(IM101682)

Procedure	Day 1	Day 2	Day 4	Day 8	Day 15	Day 22	Day 29 ± 2 Days	Day 43 ± 2 Days	Day 57 ± 2 Days	Day 71 ± 2 Days Study Discharge ^a	Notes
Blood Sampling for Immunogenicity Assessment	X				X		X		X	X	On Day 1, the immunogenicity sample should be drawn at predose. See Section 9.8.2 . Participants who seroconvert and continue to have a high titer at study discharge that is considered to be significantly increased versus baseline will be asked to return for follow-up assessment(s) for anti-abatacept antibodies approximately every 4 months until their titers and/or sero-status are judged to be stable by the investigator.
											
Clinical Drug Supplies											
Randomize	X										Participants will be randomized prior to dosing.
Study Treatment Administration ^d	X										Supplied by BMS.

^a Evaluations performed prior to study discharge, or for participants who are prematurely discontinued.

^b Measurements at predose, 30 minutes (end of infusion), and 60 minutes after the start of the infusion

^c Prior to dosing and 3 hours after the start of the infusion

- ^d Participants will be randomized to receive a 30-minute IV infusion of single dose (750 mg) abatacept drug product converted from drug substance by a new process (Treatment A), or a 30-minute IV infusion (750 mg) abatacept drug product converted from drug substance by the current process (Treatment B).

In the event that multiple procedures are required at a single time point, the ECG may be obtained up to 15 minutes earlier, vital signs may be obtained up to 10 minutes earlier or later, and clinical laboratory sample may be obtained up to 5 minutes earlier than the nominal time point, ensuring the pharmacokinetic (PK) samples can be collected on time.

For the predose assessments on Day 1 PK, immunogenicity, and PD samples, ECG, vital signs, and examinations may be obtained up to 60 minutes prior to study treatment administration.

[REDACTED]

[REDACTED]

[REDACTED]

This study is in healthy participants, a population that would not receive any health benefit from participating in this study. Although this single dose study for normal healthy participants should not pose an unacceptable health risk to participants based on the established safety profile of abatacept, in order to minimize the overall risk to participants, this protocol has inclusion and exclusion criteria appropriate to the population and proposed dosing, exclusionary screening tests (tuberculosis testing, chest x-ray, medical history, physical examination), and specific follow-up safety assessments. Adverse events and SAEs will be reviewed on an ongoing basis by the BMS Medical Monitor and by the BMS Pharmacovigilance Department to look for trends and any safety issues.

Risks from the PK, immunogenicity, and clinical safety phlebotomy procedures are standard and include infection, bleeding, bruising, blood clot formation, discomfort at the injection site, and (rarely) fainting.

More detailed information about the known and expected benefits and risks and reasonably anticipated AEs of abatacept may be found in the Investigator’s Brochure⁴, an addendum to the Investigator’s Brochure³³, and the prescribing information.¹

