Physical examinations, vital sign measurements, 12-lead electrocardiograms (ECG), and clinical laboratory evaluations will be performed at selected times throughout the dosing interval. Participants will be closely monitored for adverse events throughout the study. Blood samples for PK analysis, immunogenicity, [REDACTED] will be collected for up to 1680 hours (70 days) after study treatment administration. Approximately 260 mL of blood will be drawn from each participant during the study.

Participants will be closely monitored for AEs throughout the duration of the study. Participants will be discharged from the study following completion of evaluations on Day 71.

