7.1 Treatments Administered

The selection and timing of dose for each participant is as follows:

Table 7.1-1: Selection and Timing of Dose

Study Treatment	Unit dose strength(s)/Dosage level(s)	Dosage formulation Frequency of Administration	Route of Administration
A	750 mg	Single 30-minute infusion on Day 1	IV
B	750 mg	Single 30-minute infusion on Day 1	IV

Abbreviations: A = IV infusion of single dose (750 mg) abatacept drug product converted from drug substance by a new process; B = IV infusion of single dose (750 mg) abatacept drug product converted from drug substance by the current process; IV = intravenous

In the morning on Day 1, after fasting for at least 1 hour, each participant will receive a single IV dose of abatacept.

The start time of the IV dose administration will be called “0” hour.

Restrictions related to food and fluid intake are described in [Section 6.3](#).

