9.2.1 Time Period and Frequency for Collecting AE and SAE Information

Sections 5.6.1 and 5.6.2 in the Investigator Brochure (IB) represent the Reference Safety Information to determine expectedness of SAEs for expedited reporting.

All SAEs must be collected from the time of signing the consent, including those thought to be associated with protocol-specified procedures and within 101 days of discontinuation of dosing.

The investigator must report any SAE that occurs after these time periods and that is believed to be related to study treatment or protocol-specified procedure (eg, a follow-up skin biopsy).

All nonserious AEs must be collected at the start of study treatment until the timepoints specified in the Schedule of Activities ([Section 2](#)).

- Medical occurrences that begin before the start of study treatment but after obtaining informed consent will be recorded on the appropriate section of the eCRF module.
- All SAEs will be recorded and reported to Sponsor or designee within 24 hours, as indicated in [Appendix 3](#).
- The investigator will submit any updated SAE data to the sponsor or designee within 24 hours of updated information being available.

Investigators are not obligated to actively seek AEs or SAEs in former study participants. However, if the investigator learns of any SAE, including a death, at any time after a participant has been discharged from the study, and he/she considers the event reasonably related to the study treatment or study participation, the investigator must promptly notify the sponsor.

The method of evaluating, and assessing causality of AEs and SAEs and the procedures for completing and reporting/transmitting SAE reports are provided in [Appendix 3](#).

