- ^b Hormonal contraception may be susceptible to interaction with the study treatment, which may reduce the efficacy of the contraceptive method. Hormonal contraception is permissible only when there is sufficient evidence that the IMP and other study medications will not alter hormonal exposures such that contraception would be ineffective or result in increased exposures that could be potentially hazardous. In this case, alternative methods of contraception should be utilized.
- ^c Intrauterine devices and intrauterine hormone releasing systems are acceptable methods of contraception in the absence of definitive drug interaction studies when hormone exposures from intrauterine devices do not alter contraception effectiveness

Less Than Highly Effective Contraceptive Methods That Are User Dependent

Failure rate of >1% per year when used consistently and correctly.

- Male or female condom with or without spermicide. Male and female condoms cannot be used simultaneously
- Diaphragm with spermicide
- Cervical cap with spermicide
- Vaginal Sponge with spermicide
- Progestogen-only oral hormonal contraception, where inhibition of ovulation is not the primary mechanism of action

Unacceptable Methods of Contraception

- Periodic abstinence (calendar, symptothermal, post-ovulation methods)
- Withdrawal (coitus interruptus).
- Spermicide only
- Lactation amenorrhea method (LAM)

CONTRACEPTION GUIDANCE FOR MALE PARTICIPANTS WITH PARTNER(S) OF CHILD BEARING POTENTIAL.

Male participants with female partners of childbearing potential are eligible to participate if they agree to the following during the treatment and until the end of relevant systemic exposure.

- Inform any and all partner(s) of their participation in a clinical drug study and the need to comply with contraception instructions as directed by the investigator.
- Male participants are required to use a condom for study duration and until the end of relevant systemic exposure defined as 85 days after the end of treatment plus an additional 90 days for a total of 175 days.
- Female partners of males participating in the study to consider use of effective methods of contraception until the end of relevant systemic exposure defined as 85 days after the end of treatment in the male participant.

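### Protocol Table 2-1 and Section 9.2.1 give different end dates for SAE collection in dosed participants who leave the study early

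*Protocol*

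**What the plan says.** **Schedule (Protocol Section 2).** The SAE note in Table 2-1 runs collection from "written consent until 101 days post dose". The next sentence reads: "If a participant prematurely discontinues, all SAEs must be collected 30 days post last visit". The SAE row of Table 2-2, which covers Day 1 to Day 71, says only "See note in screening procedures", so both sentences apply to people who have been dosed.

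**Protocol Section 9.2.1.** "All SAEs must be collected from the time of signing the consent, including those thought to be associated with protocol-specified procedures", with the end of the window set at "within 101 days of discontinuation of dosing". Early discontinuers are not treated separately. The same section requires later SAEs to be reported if they are believed related to treatment or a protocol procedure. It also says investigators have no duty to look actively for events in former participants.

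**Dosing and discharge.** Table 7.1-1 gives the regimen for both treatments as "Single 30-minute infusion on Day 1". Section 5.1 says: "Participants will be discharged from the study following completion of evaluations on Day 71".

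**Leaving treatment or the study.** Protocol Sections 8.1 and 8.2 keep participants who ask to stop treatment in follow-up unless they withdraw consent for contact. Section 8.1.1 says only that follow-up may continue. Section 7.2 separately provides for discontinuation from the study because of an adverse event.

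**SAP.** Section 6.6.2 lists all reported SAEs. Section 6.6.3 assigns events after discharge to the treatment received for up to 56 days after study drug ended; later events appear in the listing of all AEs.

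**The concern.** Two passages in force give different cut-offs for the same people. A site that follows the schedule can close SAE collection weeks before a site that follows Section 9.2.1, and neither would be deviating from the text it was reading.

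A window tied to the last visit also sits oddly with this design. In a multiple-dose study, leaving early usually means dosing stopped early, so a window counted from exit keeps roughly the same distance from the last dose. Here dosing is over on Day 1 for everyone. Leaving early shortens observation without moving the end of dosing.

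At stake is the completeness of the SAE record behind a secondary objective, the safety of the new process versus the current one. If the schedule is followed as written, the SAE observation period varies with the date of exit, and the SAP cannot list an event that was never collected.

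**Working it through.** This is day arithmetic; the plan has no figure of its own to reproduce.

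**Inputs**
- Dose on Study Day 1, once (Protocol Table 7.1-1). Days post dose = study day − 1.
- Section 9.2.1 end: 101 days after dosing ends, so 101 days post dose for every dosed participant.
- Table 2-1 end for premature discontinuation: last visit + 30 days.
- Visit days from Table 2-2: 2, 4, 8, 15, 22, 29, 43, 57, 71 (±2 days from Day 29 on).
- SAP Section 6.6.3 assignment limit: 56 days after study drug.

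**Formulas**, for a last visit on Study Day d
- End of collection under the 30-day rule = (d − 1) + 30 = d + 29 days post dose.
- Shortfall against Section 9.2.1 = 101 − (d + 29) = 72 − d.

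| Last visit (study day) | 30-day rule ends (days post dose) | Short of 101 days by | Reaches 56 days? |
|---|---|---|---|
| 2 | 31 | 70 | no |
| 4 | 33 | 68 | no |
| 8 | 37 | 64 | no |
| 15 | 44 | 57 | no |
| 22 | 51 | 50 | no |
| 29 | 58 | 43 | yes |
| 43 | 72 | 29 | yes |
| 57 | 86 | 15 | yes |
| 71 | 100 | 1 | yes |

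**Reading the table**
- At scheduled discharge the two rules agree to within a day: 71 + 29 = 100. Over the ±2-day window the range is 69 + 29 = 98 to 73 + 29 = 102. This would fit the 30-day figure having been set with a Day 71 last visit in mind, but the documents do not say so.
- At every earlier scheduled visit the rules diverge. For a Day 2 exit the window is 31/101, about 31% of the Section 9.2.1 window.
- The 30-day rule reaches the SAP's 56 days only if d + 29 ≥ 56, that is d ≥ 27. Last visits up to Day 22 therefore also fall short of the SAP's own limit.
- The 56-day rule is a third window. A Day 71 discharge is already 70 days post dose, so for completers no event after discharge can fall inside it.

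**Who is affected**
- Participants whose infusion is stopped but who attend through Day 71 reach about 100 days under either rule.
- Participants who withdraw consent for all contact cannot be followed under either rule.
- That leaves dosed participants who leave the study but remain contactable. Protocol Sections 7.2 and 8.1.1 show the group is not empty. The documents give no dropout rate from which to size it.

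**The case against.** The strongest case on the other side is that the passage is ambiguous and the loss is small.

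- **The sentence may be meant as an addition.** It follows a statement that all SAEs are collected to 101 days, contains no word such as only or instead, and sits in the screening table. A participant who leaves before dosing has no dose to count from, so a rule based on the last visit would make sense there. This is plausible, but the text does not limit the sentence to that case, and Table 2-2 applies it to dosed participants. The ambiguity is the defect.
- **Later SAEs are not all lost.** Section 9.2.1 still requires related ones to be reported, and Section 9.2.3 requires SAEs to be followed to resolution, stabilization, another explanation or loss to follow-up. This stands. What can be missed is mainly a new late SAE judged unrelated or never known to the site. No visit is scheduled after Day 71 for completers either, so their last month also appears to depend on events reaching the site.
- **Follow-up is protected elsewhere.** This stands for people who only stop treatment (Sections 8.1 and 8.2). It does not settle the rule for people who leave the study.

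Stronger readings are tempting, but the documents do not support them:

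- A reader might infer that the shortest follow-up falls on those most likely to have had problems. Section 8.1 lists adverse events beside participant request, non-compliance, pregnancy, imprisonment and investigator discretion, and no discontinuation data are given. The group may include people who left because of an adverse event; no more can be said.
- A reader might infer bias between arms. The rule is the same in both, the SAP specifies no formal between-arm safety test, and nothing in the documents makes early exit differ by arm.
- A reader might point out that exits up to Day 43 (72 days post dose) close before 85 days, given the wording "until the end of relevant systemic exposure defined as 85 days after the end of treatment" in Appendix 4. That definition serves the contraception rules and is not a safety follow-up standard. The mismatch does not need it.

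**Conclusion.** The point holds as an internal inconsistency. For dosed participants who leave early, the schedule and Section 9.2.1 give SAE end dates that differ by 70 days for a last visit on Day 2, 64 on Day 8, 43 on Day 29 and 29 on Day 43. They all but coincide only at Day 71. For last visits up to Day 22 the schedule's rule also stops before the SAP's 56-day assignment limit.

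The practical consequence is limited: possible loss of some late, unrelated or unknown SAEs in a small group of unstated size. It is still worth correcting, because the rule followed as written shortens safety ascertainment for some dosed people and the remedy is a wording change.

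This rests on three readings: that the end of dosing in Section 9.2.1 means Day 1 for everyone, that the last visit is the last one attended, and that Table 2-2's cross-reference carries the whole Table 2-1 note. The documents show that the passages must be reconciled.

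**What to change.** 1. Reconcile the SAE notes in Tables 2-1 and 2-2 with Protocol Section 9.2.1, so that one SAE end date, counted from dosing, applies to every dosed participant whether or not they leave early, unless consent for contact is withdrawn.
2. If the sentence counting 30 days from the last visit was meant for people never dosed, say so and limit it to them.
3. Check that the 56-day assignment rule in SAP Section 6.6.3 is consistent with the reconciled window, and state how SAEs between 56 days and the end of collection are presented.

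The cost is one sentence in the schedule note, a check of one SAP sentence, and a later SAE cut-off for a few early discontinuers. No visits or procedures are added.

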4 OBJECTIVES AND ENDPOINTS

Table 4-1: Objectives and Endpoints

Objectives	Endpoints

Primary
 
To compare the PK of the abatacept drug product converted from drug substance by a new drug substance process (Treatment A) relative to the current drug substance process (Treatment B) following a single dose (750 mg) IV infusion in healthy participants.
	
Cmax and AUC(INF) of abatacept

Secondary
 
To assess the safety of a single dose (750-mg) IV infusion of the abatacept drug product converted from drug substance by a new drug substance process (Treatment A) versus drug substance by the current drug substance process (Treatment B).
 
To assess the immunogenicity of abatacept drug product converted from drug substance by a new drug substance process (Treatment A) versus drug substance by the current drug substance process (Treatment B).
 
To characterize the PK of abatacept drug product converted from drug substance by a new drug substance process (Treatment A) versus drug substance by the current drug substance process (Treatment B).
	
Safety assessments will be based on medical review of AE reports, vital sign measurements, ECGs, physical examinations, and clinical laboratory tests.
 
Immunogenicity determination will be based on the incidence of laboratory-reported positive responses and titers of anti-abatacept antibodies specific for “CTLA4 and possibly Ig” and “Ig and/or Junction Region.”
 
Tmax, AUC(0-T), AUC(0-28 day), CLT, Vss, and T-HALF of abatacept

Table 4-1: Objectives and Endpoints

Objectives	Endpoints
[REDACTED]	[REDACTED]

Abbreviations: AUC(0-28 day) = area under the serum concentration-time curve from time zero to 28 days after dosing; AUC(0-T) = area under the serum concentration-time curve from zero to the last time of the last quantifiable concentration; AUC(INF) = area under the serum concentration-time curve from time zero extrapolated to infinity; CD86 = cluster of differentiation 86; CLT = total body clearance; Cmax = maximum observed serum concentration; CTLA-4-T = cytotoxic T lymphocyte (T cell)-associated antigen 4; ECG = electrocardiogram; IV = intravenous; PD = pharmacodynamic; PK = pharmacokinetic; T-HALF = terminal phase elimination half-life in serum; Tmax = time of maximum observed serum concentration; Vss = volume of distribution at steady-state.

